4.6 Steps to Control or Mitigate Risks

Subjects with no aspirin resistance, allergy, or bleeding risk will continue on aspirin indefinitely and either clopidogrel (75 mg/day), prasugrel (5-10 mg/day), or ticagrelor (90 mg bid) for at least six months following stent implantation. In accordance with the PCI recommendations from ACCF/AHA/SCAI, it is recommended that dual anti platelet therapy (DAPT) be continued for 6 months (12 months in ACS patients) following stent implantation (1) unless an intervening medical necessity, such as severe bleeding, occurs. If DAPT is discontinued before 6 months (or 12 months in ACS patients) due to medical necessity (for example, severe bleeding), the reason should be documented.

The investigational plan is specifically designed to manage and minimize risks through careful subject selection, thorough training of investigators, adherence to the pre-determined time points to assess subject clinical status and regular clinical monitoring visits by Sponsor appointed monitoring personnel.

In addition, an independent Data Safety Monitoring Board (DSMB) will monitor safety of the subjects throughout the trial.

4.7 Risk-to-Benefit Rationale

The EluNIR represents a potential advance in both stent and delivery system design and is expected to be noninferior to second generation DES such as the Resolute. Subjects enrolled in this trial have an indication for PCI due to significant coronary stenosis. The majority of risk associated with the trial is inherent to standard of care PCI and is not likely to be increased by participation in this trial. While there may be unknown risks associated with the long EluNIR stent these are mitigated by the use of an approved stent platform and delivery system with a polymer coating (Carbosil) which is biocompatible and thrombo-resistant. Ridaforolimus is part of the rapamycin analog family of drugs for which there is extensive experience on DES.

5 OBJECTIVES AND HYPOTHESES OF THE CLINICAL INVESTIGATION

5.1 Objectives

To further assess the safety and efficacy of the long (38 mm) Ridaforolimus Eluting Stent – EluNIR.

5.2 Claims and Intended Performance of the Study Device

The EluNIR Ridaforolimus Eluting Coronary Stent System is indicated for improving coronary luminal diameter in patients with heart disease including angina (stable or unstable), silent ischemia (in absence of symptoms a visually estimated target lesion diameter stenosis of $\geq 70\%$), a

positive non-invasive stress test, or FFR ≤ 0.80 must be present), NSTEMI, or recent STEMI due to de novo lesions in vessels with reference diameters of 2.75 mm to 4.25 mm.

5.3 Risks and Anticipated Adverse Device Effects That Are To Be Assessed

The risks and anticipated adverse device effects are summarized in Section 14.6 as well as in the IB. All Adverse Device Effects (ADE) will be collected and assessed as such, based on initial assessment of the Investigator, as well as the appointed Medical Monitor, whether the adverse event is or is not related to the device.

6 DESIGN OF THE CLINICAL INVESTIGATION

6.1 General

6.1.1 Description of Trial

The BIONICS 38 mm Trial will enroll approximately 50 subjects with a wide spectrum of PCI indications (stable angina as well as ACS, including subacute STEMI (>24 hours since first hospital presentation) as well as complexity.

This is a prospective, multi-center, single-arm, open-label clinical trial.

6.1.2 Rationale for Trial

Drug eluting stents have significantly lowered the restenosis rate following PCI. Because of delayed re-endothelialization, however, prolonged (current recommendations are for 12 months) dual anti-platelet therapy (DAPT) is indicated, but has not completely eliminated stent thrombosis, a serious complication with potential mortality. Rates for stent thrombosis with second generation DES have been in the range of 1-3% at one year after stent implantation.

Long-length stenting has particularly poor outcomes when bare metal stents are used (6). Moreover, treatment of a long coronary lesion with multiple stents, has been associated with serious complications such as significantly increased risk of stent thrombosis or restenosis at the gap between adjacent stents (7), as the vessel is exposed to more stent's struts, polymer, and larger drug dose is delivered to the to the intima at the site of the stent's overlap (8). As such, implanting long DES, could potentially reduce the need to use multiple stents in long coronary lesions. The maximum stent length available for current stent platform is 38 mm and thus overlapping stents are often required to cover longer segments (8). In addition, in a post-hoc analysis from the BIONICS Trial, the 12-month target lesion failure (TLF) outcomes, for patients with long lesions -exceeding 30 mm- who were treated either by Ridaforolimus-Eluting stent or Zotarolimus-Eluting stent, were similar supporting the safety and efficacy of Ridaforolimus-Eluting stent in patients with complex long lesions

Rates for restenosis as well as ST vary between stents and depend on a myriad of factors including stent design (for example, open- vs. closed-cell), strut thickness, stent material, flexibility of the stent, and degree of mal-apposition. It is therefore important to examine the safety and efficacy of the long (38 mm) EluNIR stents. Comparisons focus on clinical events, primarily target lesion

failure (TLF), defined as the composite of cardiac death, target vessel related MI, or ischemia driven target lesion revascularization.

The present trial is a companion trial to the BIONICS and NIREUS trials aimed at further assessing the safety and efficacy of the long (38 mm) EluNIR stent.

6.1.3 Primary and Secondary Endpoints

Definitions of terms and endpoints are located in Section [19.1](#). Acronyms and abbreviations are defined in Section [19.2](#).

6.1.3.1 Primary Endpoint

Combined efficacy and safety endpoint:

Device success as determined by the Angiographic Core Lab (ACL) with no 30 day MACE.

Device success is defined as achievement of a final in-stent residual diameter stenosis of <30% (by QCA), using the EluNIR 38 mm stent only and without a device malfunction.

MACE is defined as the composite of cardiac death, any MI, or ischemia-driven TLR.

6.1.3.2 Secondary Endpoints

- Device success
- Lesion success
- Procedure success

As determined by the Angiographic Core Laboratory at the time of the baseline procedure.

Secondary endpoints to be evaluated at 30 days, 6 months and 1 year:

- Target lesion failure (TLF; the composite cardiac death, target vessel related MI, or ischemia-driven TLR)
- Target vessel failure (TVF; the composite rate of death, target vessel related MI or ischemia-driven TVR)
- Major adverse cardiac events (MACE; the composite rate of cardiac death, any MI or ischemia-driven TLR)
- All-cause mortality
- Cardiac death
- Myocardial infarction
- Target vessel related MI
- Ischemia-driven TLR
- Ischemia-driven TVR
- Stent thrombosis (ARC definite and probable)

6.1.4 Methods and Timing for Assessing, Recording, and Analyzing Variables

Data collection commences after the subject has provided an informed consent. Data collection including subject demographic information, laboratory tests, and procedural data as well as follow-up visits or telephone contacts will be conducted by an Investigator or site coordinator who has been trained on the CIP and Case Report Forms (CRF).

Data required for analysis will be obtained as outlined in **Table 1**. After discharge from the hospital, each subject will be followed with an in-clinic follow-up visit at 30 days, and follow-up by phone at 6 months and 1 year post procedure.

Table 1: Schedule of Data Collection

TYPE OF DATA TO BE COLLECTED	Pre-Procedure ¹ (within 30 days)	Pre-Procedure ¹ (within 24 hours)	Baseline Procedure	Post-Procedure	30 days (± 7 days)	6 Months (± 30 days) by phone	1 year (-30 days / +14 days) by phone	Unscheduled visits
Patient Informed Consent				✓				
Patient Medical/Clinical History				✓ ¹				
Angina Status		✓ ¹		✓ ¹	✓	✓	✓	✓
General Eligibility Criteria			✓ ¹					
Angiographic Eligibility Criteria			✓ ¹					
Clinical Laboratory Tests:								
CBC, Creatinine, BUN	✓ ^{1,2}							
Lipid profile	✓ ^{1,2}							
CK, CK-MB or Troponin		✓ ¹⁻³		✓ ⁴				
12-Lead ECG		✓ ¹		✓				
Coronary Angiogram & PCI			✓ ¹					
Study Stent Information			✓ ¹					
Per Protocol DAPT Medications ⁵		✓ ¹	✓ ¹	✓	✓	✓	✓	✓
Concomitant Cardiac Medications ⁶		✓ ¹		✓	✓	✓	✓	✓
Adverse Events Monitoring			✓ ^{1,7}	✓	✓	✓	✓	✓

1. Data will be collected only after post-procedural informed consent has been obtained.
2. Should be collected at time of enrollment if not collected at baseline as part of routine SOC.
3. Within 24 hours pre-procedure if collected per site protocol. For subjects with ACS, it is recommended that enzyme levels be within 8 hours of the procedure or have already been shown to be decreasing. For STEMI patients enzyme levels should have peaked for either CK-MB or Troponin (I or T) or both.
4. If Troponin is elevated or CK-MB is elevated \geq upper limit of normal, serial measurements of CK and CK-MB (preferred) or Troponin (I or T) must be done until a decline is noted
5. Clopidogrel 75 mg daily or prasugrel 5 to 10 mg daily or ticagrelor (90 mg bid) must be given for a minimum of 6 months (12 months in ACS patients) as well as aspirin 75 to 100 mg daily to be taken indefinitely.
6. Concomitant cardiac medications will be recorded by categories (e.g., statin, non-statin lipid lowering, ACE inhibitors, ARBs, beta-blockers, calcium channel blockers, other anti-anginals).
7. All adverse events that occur after EluNIR stent was inserted into the patient's target artery (beyond the guiding catheter) will be recorded.

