6.1.4.4 Post-Procedure and Discharge

- Enrollment and study stent information

Subject information will include the following. Refer to Section 19.1 for definitions.

- Demographics (e.g., age, gender, height, weight)

- Risk factors (dyslipidemia, hypertension, family history of premature coronary disease, tobacco use, and diabetes)
- Cardiac history (previous MI, intervention history, and past angina status according to CCS and Braunwald classifications)
- Baseline (pre-procedure) angina status
- DAPT medications (pre-procedure)
- Concomitant cardiac medication by category
- Assurance that informed consent has been obtained correctly

Collection of pre-procedure laboratory assessments and ECG data (if were done; if missing can be obtained as soon as possible after enrollment).

Angiographic data:

- Target lesion location
- Non-target vessel treatment, if applicable
- Anticoagulation administration
- Procedural complications that occur after the long EluNIR stent was advanced beyond the guiding catheter.
- Per-protocol DAPT medications
- Adverse events that occur after the long EluNIR stent was advanced beyond the guiding catheter.

Subjects who undergo PCI with a long EluNIR stent but do not consent to be enrolled in the study will not be included in the study and their data will not be collected.

- Post-PCI 12 lead ECG
- Post-PCI angina status
- Post-PCI adverse events with related laboratory tests results and details of any subsequent repeat coronary angiography and results of such, if applicable
- Post-PCI per-protocol DAPT medications
- Post-PCI concomitant cardiac medication by category
- CK and CK-MB or Troponin (I or T). Two post-PCI measures are recommended, but if early discharge is contemplated, at least one post procedure measurement 6-10 hours post-PCI is mandatory with the results known before discharge. The need for further cardiac biomarker measurement will be determined by the biomarker level, as detailed below in [Table 2](#):

Table 2: Patient Status as Indicated by Biomarker Levels

Biomarker Level	Patient Status	Action
<ULN CK-MB or Troponin* <7X ULN and	Clinically stable**	The patient may be discharged without additional levels.

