1-3x ULN CK-MB or Troponin* 7-20X ULN and	Clinically stable**	The patient may be discharged but a second level is required at 12-18 hours prior to discharge. If the patient had an elevated troponin level immediately prior to study PCI and post-PCI level is lower than the immediate pre-PCI level, a second level is not required.
≥3x ULN CK-MB or Troponin* >20 X ULN	Not clinically stable	The patient may not be discharged until serial CK-MB or Troponin levels are decreasing and the patient is stable. If the patient had an elevated troponin level immediately prior to study PCI and post-PCI level is lower than the immediate pre-PCI level, a second level is not required.

*using conventional or hs-troponin assays with 99th percentile cutoff of 14 ng/L to 70 ng/L

** clinically stable- no chest pain, no ECG changes, no hypotension and no overt bleeding

6.1.4.5 30 Days (± 7 days)

- Angina status
- Adverse events with related laboratory tests results, ECGs, details of any subsequent myocardial infarction, hospitalization, or repeat coronary angiography and results of such, if applicable
- Details of any subsequent coronary interventions (e.g., repeat PCI or CABG)
- Compliance to protocol-required DAPT medications
- Use and changes in chronic antiplatelet medication regimen. Data are collected for the duration of the trial
- Concomitant cardiac medication by category

6.1.4.6 6 months (± 30 Days) & 1 year (±30 Days) Follow-up (by phone)

- Angina status
- Adverse events with related laboratory tests results, ECGs, details of any subsequent myocardial infarction, hospitalization, or repeat coronary angiography and results of such, if applicable
- Details of any subsequent coronary interventions (e.g., repeat PCI or CABG)
- Compliance to protocol-required DAPT medications
- Use and changes in chronic antiplatelet medications. Data are collected for the duration of the trial
- Concomitant cardiac medication by category

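### Two conflicting rules for post-PCI biomarker sampling: the Table 1 footnote demands a decline, Table 2 row 2 does not, so periprocedural MI can be under-counted, realistically in the CK-MB ≥3x ULN sensitivity analysis

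*Protocol*

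**What the plan says.** Protocol Section 6.1.4 introduces Table 1 with the words "Data required for analysis will be obtained as outlined in" that table. Its footnote 4 covers post-procedure biomarkers. If troponin is elevated, or CK-MB is at or above ULN, "serial measurements of CK and CK-MB (preferred) or Troponin (I or T) must be done until a decline is noted". SAP Section 4.5, Table 3, footnote 4 carries the same rule. The SAP does not reproduce protocol Table 2.

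Protocol Section 6.1.4.4 sets a different rule for the same samples. The minimum is: "Two post-PCI measures are recommended, but if early discharge is contemplated, at least one post procedure measurement 6-10 hours post-PCI is mandatory". Then: "The need for further cardiac biomarker measurement will be determined by the biomarker level, as detailed below in" Table 2. The rows of Table 2 are:

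- Row 1 (CK-MB below ULN or troponin <7x ULN, clinically stable): "The patient may be discharged without additional levels".
- Row 2 (CK-MB 1-3x or troponin 7-20x ULN, clinically stable): "The patient may be discharged but a second level is required at 12-18 hours prior to discharge". The second level is waived if the post-PCI level is below an elevated pre-PCI troponin.
- Row 3 (CK-MB ≥3x or troponin >20x ULN; status cell "Not clinically stable"): "The patient may not be discharged until serial CK-MB or Troponin levels are decreasing and the patient is stable".

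Protocol Section 19.1 judges periprocedural MI on the peak within 48 hours. SAP Section 5.6.3 uses the highest post-procedure value within 48 hours. Any MI within 30 days counts in MACE and hence in the primary endpoint (protocol Section 6.1.3.1). Protocol Section 7.2.2 and SAP Section 5.2.2 add sensitivity definitions at CK-MB ≥5x and ≥3x ULN, for subjects with a normal baseline CK-MB and with no clinical signs needed.

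**The concern.** A stable patient with CK-MB between 1x and 3x ULN must be followed to a decline under footnote 4. Under Table 2 the same patient may go home after a second value that is still rising. Table 2 is not only a discharge guide, because Section 6.1.4.4 makes it the rule for further measurement. A site that does exactly what Table 2 requires, and no more, therefore breaches footnote 4. The analysis plan meanwhile presumes sampling that Table 2 does not secure.

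The endpoint depends on a maximum, so stopping early biases it one way, towards fewer MIs and a higher success rate. There is no control arm to share that bias. Sites may also differ in which rule they follow, and Section 7.8 allows up to 20 of the roughly 50 subjects at one center.

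**Working it through.** The plan gives no figure for this point, so there is none to reproduce. The inputs are the two sampling rules, the MI thresholds (Sections 7.2.2 and 19.1) and n = 50.

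**1. Where the rules differ (clinically stable patients)**

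| Post-PCI value | Footnote 4 | Table 2 | Conflict? |
|---|---|---|---|
| CK-MB <ULN, troponin not elevated | Not triggered | No further level | No |
| Troponin >ULN to <7x | Serial to decline, if elevated means above ULN | No further level | Only on that reading |
| CK-MB 1-3x | Serial to decline | One second level | Yes |
| Troponin 7-20x | Serial to decline | One second level | Yes |

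The row 2 waiver is itself evidence of a decline, so it is not part of the conflict. A second CK-MB of ≥3x would arguably move the patient to row 3. What remains in row 2 is a second value below 3x that is not falling.

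**2. Direction**

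The maximum of a subset of samples cannot exceed the maximum of the full set. Stopping before a decline can leave the recorded peak unchanged or lower it, but cannot raise it.

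**3. Further CK-MB rise needed after the last required sample**

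Fold-rise = threshold / last value (normal baseline; last values chosen to span row 2):

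| Last CK-MB (x ULN) | To ≥3x | To ≥5x | To ≥10x (main definition) |
|---|---|---|---|
| 1.0 | 3/1.0 = 3.00 | 5.00 | 10.00 |
| 2.0 | 3/2.0 = 1.50 | 2.50 | 5.00 |
| 2.5 | 3/2.5 = 1.20 | 2.00 | 4.00 |
| 2.9 | 3/2.9 = 1.03 | 1.72 | 3.45 |

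From any value below 3x, the rise to 5x exceeds 5/3 = 1.67-fold and the rise to 10x exceeds 10/3 = 3.33-fold.

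**4. Troponin under the main definition (no CK-MB measured, normal baseline)**

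From row 2 the rise to 70x is at least 70/20 = 3.5-fold. From row 1 it is more than 70/7 = 10-fold. The lower main thresholds (CK-MB 5x, troponin 35x) need new Q waves or LBBB. Table 2 defines clinical stability as including no ECG changes, so they are not met when sampling stops.

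**5. Time left unsampled in the 48 hours**

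If the row 2 interval of 12-18 hours is counted from PCI (an assumption, since the text counts it back from discharge), 48 − 18 = 30 to 48 − 12 = 36 hours remain. On the minimum single-sample route in row 1, 48 − 10 = 38 to 48 − 6 = 42 hours remain.

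**6. Effect on the reported rate**

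Each subject who changes from success to failure moves the rate by 1/50 = 2.0 points. As an illustration, assume 46/50 successes in the ≥3x analysis and 0 to 3 missed MIs. Neither figure comes from the documents.

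| Missed MIs | Success | Exact 95% CI |
|---|---|---|
| 0 | 46/50 = 92.0% | 80.8-97.8 |
| 1 | 45/50 = 90.0% | 78.2-96.7 |
| 2 | 44/50 = 88.0% | 75.7-95.5 |
| 3 | 43/50 = 86.0% | 73.3-94.2 |

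**The case against.** The strongest reply is that both rules can be obeyed. Rows 1 and 2 permit discharge, while footnote 4 is mandatory, so a site following the footnote breaks nothing in Table 2. That is true, but it does not work in reverse. Section 6.1.4.4 tells sites that Table 2 settles the need for more samples, and a site that relies on it falls short of the footnote.

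Second, the consequence is small. The trial is descriptive, with no hypothesis test. The exposed patients are stable, and suspected ischemic events at unscheduled visits require biomarkers and an ECG (Section 6.1.4.7). This stands for the main definition. It does not remove the exposure at ≥3x, where no signs or symptoms are required.

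Third, four stronger conclusions that a reader might draw are not supported:

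- That the primary endpoint is materially biased. The rises in steps 3 and 4 make that unlikely under the main definition.
- That every patient with an elevated troponin would yield the CK-MB values that the ≥3x and ≥5x analyses use. Footnote 4 is also met by serial troponin alone, so at a troponin-only site enforcing it need not add an event there.
- That row 1 certainly conflicts. Footnote 4 does not define an elevated troponin, and the <7x tier may be a deliberate clinical cut-off.
- That a stable patient at CK-MB ≥3x falls outside every row. The row 3 status cell may simply have lost a connective in the table layout, so nothing here rests on it.

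**Conclusion.** The plan is wrong as written, because two rules for the same samples conflict. The severity is minor. The row 2 conflict for CK-MB 1-3x ULN needs no assumption. The row 1 conflict holds only if elevated troponin means above ULN.

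The direction is certain: relative to footnote 4, periprocedural MI can only be under-counted. The size is not. The realistic exposure is the CK-MB ≥3x sensitivity analysis, where a value close to 3x needs little further rise. The ≥5x analysis is less exposed, and the effect on the main SCAI-based primary endpoint is likely very small. The number of affected subjects cannot be derived from the documents, and the 0 to 3 range only shows the scale.

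Two groups are not sized. Subjects with elevated baselines are judged on increments, and the 3rd Universal Definition's threshold is not given in the documents. SAP Section 5.6.3 will show how many subjects peaked at 1-3x, but not whether that value was still rising.

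**What to change.** - **Table 2 row 2:** if the second level is not lower than the first, continue serial levels (CK-MB preferred) until a decline is noted. Keep the waiver for a post-PCI level below an elevated pre-PCI troponin.
- **Protocol Table 1 footnote 4 and SAP Table 3 footnote 4:** refer to that same rule. If row 1's exemption for troponin <7x ULN is intended, state it there as a deliberate exception.
- **Optional, beside the ≥3x analysis:** report the number of subjects with at least two post-PCI CK-MB values whose last value within 48 hours was elevated and not falling. Count single-sample subjects separately, because one value cannot show a trend.

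The cost is wording in one table and two footnotes, plus one summary line if the optional count is added. The downside is an occasional extra routine blood draw, which footnote 4 already requires, and a slightly longer stay for a few stable patients. The sample size and the planned analyses do not change.

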6.1.4.1 Pre-Procedure

Subject preparation will occur in accordance with standard hospital policy for the care of interventional cardiology patients. Written informed consent will be obtained according to Section 13, post- procedure. Pre-procedural data will be collected after informed consent has been obtained.

6.1.4.2 Pre-Procedure Laboratory Assessments

The following laboratory assessments are to be performed (having been done as part of routine clinical care) prior to the baseline procedure.

Within 30 days prior to procedure:

- Complete Blood Cell Count (CBC)
- Creatinine, BUN
- Lipid profile (total cholesterol, LDL, HDL, triglycerides)

Within 24 hours pre-procedure:

- Electrocardiogram (ECG)
- Creatine kinase (CK) and creatine kinase muscle-brain isoenzyme (CK-MB) (For subjects with ACS, enzyme levels need to be within 8 hours of the procedure or have already been shown to be decreasing.)
- Troponin (T or I) where CK-MB is not available

Note: If any of the baseline tests were not obtained prior to the PCI procedure they may be obtained (including baseline biomarkers) as soon as possible after enrollment.

